#### 8.2 Serious Adverse Event (SAE).

A serious adverse event is defined as any adverse medical event (experience) that results in at least one of the outcomes listed below:

- 1. Death
- 2. Life-threatening
- 3. Requires inpatient hospitalization or prolongation of existing hospitalization.
- 4. Results in persistent or significant disability/incapacity with substantial disruption of the ability to conduct normal life functions.
- 5. Congenital anomaly/birth defect.
- 6. A medical event that may not result in death, be life threatening, or require hospitalization may be considered an SAE when, based upon medical judgment, it may jeopardize the patient or participant and may require medical or surgical intervention to prevent one of the outcomes listed in this definition.

**Hospitalization (or prolongation of hospitalization).** For AE reporting purposes, a hospitalization is defined as an inpatient hospital stay equal to or greater than 24 hours.

### 8.3 Reporting

Adverse events will be assessed by phone in weeks 1, 3, and 5 and at the Week 6 visit. At each participant visit and phone call, the site study staff will assess adverse events by asking participants if they have experienced any new symptoms since starting the experimental treatment. They will ask specifically if any skin reactions have occurred.

All adverse events, whether observed by study staff or investigator, elicited from or volunteered by the participant, should be documented. Each adverse event will include the date of onset, date of resolution, severity, and the relationship to the study device or study procedures, and any action taken with respect to the study device or intervention.

Recording of the adverse events will occur once the participant signs the consent form until the participant goes off study.

Adverse events will be reported to the URCC NCORP Research Base using REDCap, which can be accessed from the URCC NCORP website.

#### Table 7. Reportable adverse events

Adverse Event								
Attribution	Grade 1	Grade 2	Grade 3	Grade 4	Grade 5			
Unrelated			URCC	URCC	URCC			
Unlikely			URCC	URCC	URCC			
Possible	URCC	URCC	URCC	URCC	URCC			
Probable	URCC	URCC	URCC	URCC	URCC			
Definite	URCC	URCC	URCC	URCC	URCC			

Serious adverse events requiring expedited reporting via CTEP-AERS are described below in **Section 8.4**. Serious adverse events not requiring expedited reporting through CTEP-AERS should be entered into REDCap and URCC notified within 10 calendar days of learning of the event.

All recorded adverse events reported to the URCC Research Base will be reported to the Data Safety Monitoring Committee.

All adverse events that in the opinion of the investigator are clinically significant will be documented and followed according to good medical practices.

### 8.4 Responsibilities for Expedited Reporting

URCC NCORP Research Base affiliates are required to notify the URCC Research Base if a participant has an adverse event requiring expedited reporting. All SAEs that meet expedited reporting criteria defined in the reporting table below will be reported via CTEP-AERS, the Adverse Event Expedited Reporting System, accessed via the CTEP web site, https://eapps-ctep.nci.nih.gov/ctepaers/pages/task.

Commercial reporting requirements are provided in the table below. The commercial device used in this study is the Quell TENS Device.

Table 8. Expedited reporting requirements for adverse events experienced by participants who have received study device/intervention within 30 days of the last administration of commercial study device/intervention.

Attribution	Grade 4		Grade 5(a)	
	Unexpected	Expected	Unexpected	Expected
Unrelated or Unlikely			CTEP-AERS	CTEP-AERS
Possible, Probable, Definite	CTEP-AERS		CTEP-AERS	CTEP-AERS

**CTEP-AERS.** Indicates an expedited report is to be submitted via CTEP-AERS within 10 calendar days of learning of the event (b).

- 1. This includes all deaths within 30 days of the last use of the commercial study device, regardless of attribution. Any death that occurs more than 30 days after the last use of commercial study device and is attributed (possibly, probably or definitely) to the device/intervention and is not due to cancer recurrence must be reported according to the instructions above.
- 2. Submission of the on-line CTEP-AERS report plus any necessary amendments generally completes the reporting requirements. You may, however, be asked to submit supporting clinical data to the Research Base in order to complete the evaluation of the event.

For more information see:

https://ctep.cancer.gov/protocolDevelopment/electronic\_applications/docs/aeguidelines.pdf

## 9. STUDY MONITORING

#### 9.1 Data Management Summary

This project will collect data in multiple formats: paper documents and electronic questionnaires (REDCap).

When written, hard-copy (paper) data are received at the URCC NCORP Research Base, they are processed as follows:

- 1. Data are visually checked line by line for missing, duplicate, ambiguous or unreasonable responses and if found, the originating site is queried for such data.
- 2. In response to a query, the form is amended per good clinical practice (GCP) the change is documented and the form is re-submitted to the research base.
- 3. All paper forms are scanned via Teleforms software into tables in an Access database. Again, any missing, duplicate or ambiguous data found at this step generates a query to the originating site.
- 4. The electronic database tables are visually checked, line by line, against the corresponding forms for accuracy.
- 5. Queries are also generated if data are not received within 14 days of the assessment.
- 6. When all data have been received on any given case, a chart audit is performed to ensure receipt and accuracy of all required data.
- 7. All paper documents are stored in locked file cabinets or in locked, limited access file rooms. The electronic Access databases of those scanned documents are on password protected drives located behind University of Rochester firewalls, with limited access.

Data entered into REDCap are reviewed for accuracy and stored in the University of Rochester secure REDCap database. Queries are generated for any questionable or late data.

On-site audits are conducted at least every three years in accordance with NIH/NCI Clinical Trials Monitoring Branch (CTMB) guidelines. The primary objective of an on-site audit is to document compliance of the NCORP site with protocol and regulatory requirements, verify accuracy of data by comparing submitted data to source documents at the NCORP site, and to provide information on good clinical practices in study conduct and data management. The equivalent of 10% of cases accrued at the site will be audited. All auditing is done as per NIH/NCI CTMB Guidelines.

# 9.2 Schedule of Data Collection

#### Table 10. Forms to Be Kept

FORMS	Screening	Baseline	Week 6		
Participant Forms (paper)					
On-Study		Х			
Expectation Questionnaire		Х			
EORTC CIPN20		Х	Х		
Daily Diary (CIPN symptoms / rescue medication usage)*		Х	Х		
CIPN Symptom Inventory – week recall	Х	Х	Х		
TNAS		Х	Х		
PROMIS 1		Х	Х		
PROMIS 2		Х	Х		

PROMIS 3		Х	Х
CIPN Interference Questionnaire		Х	Х
General Impression of Neuropathy			Х
General Impression of Activity			х
Blinding Questionnaire			Х
Qualitative Feedback Questionnaire			Х
Coordinator Forms (REDCap  , paper  )			•
Eligibility checklist (Medical Record, Clinician-reported, and Patient-reported items) 	х		
Consent form 	Х		
Clinical record information form 	Х		
TENS Device Settings form 		Х	
CPM data collection form 	X	Х	Х
SPPB Balance form 		Х	Х
Lower-limb sensation threshold data collection form 	X	Х	Х
Coordinator blinding question 			Х
Changes in concomitant analgesic medications form 			Х
Adverse Event (AE) Form 1**			Х
Screening log completed for patients who a Submit chemotherapy treatment notes from	are approached, l n participant's me	but not consen edical record at	ted Screening

Telephone Contact Sheet to be completed with each phone call

\* Daily diary will be completed during the week between the Screening and Baseline visits (collected at the Baseline Visit) and during Weeks 4 (i.e., day 21 - 28) and 6 (i.e., day 35 - 42) (collected at 6 Week visit).

\*\* Adverse Events are also assessed during Week 1, 3, 5 phone calls

## 9.3 Data and Safety Monitoring Plan

**Data Safety Monitoring Committee.** The Director of the URCC delegates responsibility for continued review and monitoring of all clinical trials conducted by the URCC to the James P Wilmot Cancer Center (JPWCC) DSMC. This committee provides oversight of study progress and safety by review of accrual and adverse events at annual (or biannual) meetings. Any adverse event requiring expedited review per protocol will be submitted to the JPWCC DSMC for determination as to whether further action is required. Interim meetings are scheduled, as needed, to address specific issues that require immediate attention to assure participant safety. The DSMC:

- 1. Reviews assigned clinical trials conducted at the URCC for progress and safety
- 2. Reviews all adverse events requiring expedited reporting as defined in the protocol
- 3. Reviews reports generated by the URCC data quality control review process
- 4. Submits recommendations for corrective actions to the Protocol Review Committee and the Principal Investigator

The DSMC will review study progress and cumulative reports of adverse events either bi-annually or annually (determined by the DSMC). Once the final protocol is submitted to NCI, the protocol will be submitted to the Peer Review Committee for review and frequency of review determined. An overall

assessment of accrual and adverse events will enable the committee members to assess whether significant benefits or risks are occurring that would warrant study closure. Interim meetings are scheduled, as needed, to address specific issues that require immediate attention to assure participant safety

The URCC will notify the NCORP sites immediately of any serious safety concerns identified by the DSMC. DSMC reports will be available for download on the research base website.

In general, outcome data are not made available to individuals outside of the JPWCC DSMC until accrual has been completed and all participants have completed their treatment. At this time, the JPWCC DSMC may approve the release of outcome data on a confidential basis to the trial Principal Investigator for planning the preparation of manuscripts and/or to a small number of other investigators for purposes of planning future trials. Any release of outcome data prior to the JPWCC DSMC's recommendation for general dissemination of results must be reviewed and approved by the JPWCC DSMC.

**Safety Coordinator.** All adverse events reported to URCC are entered into a REDCap database and can be monitored through automated reports. The Safety Coordinator monitors adverse event rates utilizing this database. If the study has had two or more of the same SAEs reported in a month or more than six of the same SAEs in six months, the DSMC will review the summary of SAEs, discuss events with the Study Chair, and conduct a more detailed review with the Study Chair. The Data Safety Monitoring Chair will determine if further action is required. The Safety Coordinator:

- 1. Forwards all adverse events requiring expedited reporting to the URCC Data Safety Monitoring Committee Chair who determines if immediate action is required
- 2. Maintains a database of all adverse events requiring expedited reporting
- 3. Ensures all reports are available for all meetings of the DSMC
- 4. Monitors adverse event rates utilizing the study database.

#### 9.4 Record Retention

Clinical records for all participants, including REDCap forms, all source documentation (containing evidence to study eligibility, history and physical findings, laboratory data, results of consultations, etc.), as well as IRB records and other regulatory documentation will be retained by the Investigator in a secure storage facility in compliance with Health Insurance Portability and Accountability Act (HIPAA), Office of Human Research Protections (OHRP), Food and Drug Administration (FDA) regulations and guidelines, and NCI/DCP requirements, unless the standard at the site is more stringent. Records will be retained for at least five years after the date of completion of the research. The records should be accessible for inspection and copying by authorized persons of the Food and Drug Administration.

## 10. STATISTICAL CONSIDERATIONS

**10.1 Quality Control.** Established standardized data quality procedures are used for all URCC NCORP Research Base studies. Data will be entered on scannable (Teleforms) or electronic forms in REDCap and electronically transferred to Microsoft Office databases. Data will be inspected visually. Data distributions will be evaluated to identify any outliers that will be inspected for possible mistakes. If no mistake is found for an outlier, it will remain in the data. Statistical analyses will be performed using SAS, JMP, or R as appropriate.

**10.2 Analysis set and Missing Data.** All participants who are randomized will be included in the analyses. All efforts will be made to prevent missing data. We will use multiple imputation methods that assume missing at random for the primary and secondary analyses. A sensitivity analysis using pattern mixture methodology that assumes missing not at random will be used to evaluate the impact of missingness on the results.

**10.3 Sample Size Estimation.** Since this is a phase II preliminary efficacy trial, the primary analysis will be performed at the two-tailed 20% significance level (i.e., alpha=0.2). A sample size of 126 evaluable participants will provide 80% power to detect a 0.4 effect size (standardized mean difference) in the primary analysis. Assuming 15% withdrawal, we will randomize 150 participants.

**10.4 Primary Analysis.** The effects of TENS on CIPN will be estimated using analysis of covariance (ANCOVA). The model will include CIPN20 at Week 6 as the outcome, treatment group as the factor, and study site and the baseline CIPN20 score as covariates. Additionally, to explore potential large impacts of cancer type, chemotherapy class (i.e., platinum, taxane, other), and analgesic consumption ( $\geq$ 30% vs. <30% decrease in number of days acetaminophen and/or NSAIDs were taken), we will add these factors to the above model for sensitivity analyses. We will also perform subgroup analyses separately based on these factors to identify possible differential intervention effects to inform the design of a future study. Distributional assumptions (e.g. normality of residuals) will be evaluated and, if necessary, appropriate transformations or nonparametric methods will be used.

**10.5** Secondary Analyses. ANCOVA analyses as in the primary analysis will be used for individual symptoms (i.e., hot/burning and sharp/shooting pain, numbness, tingling, and cramping (0 - 10 NRS)). For each of the symptoms, baseline and Week 6 scores will be calculated as the mean of weekly daily diary scores during the week between Screening and Baseline and Week 6, respectively.

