# 3. CHARACTERISTICS OF STUDY POPULATION

## 3.1 Inclusion Criteria

Participants must:

- 1. Have completed treatment with a platinum agent, taxane, vinca alkaloid, or bortezomib at least 3 months prior to registration. See Appendix 1 for a list of drugs included in these drug classes.
- 2. Have a clinical diagnosis of CIPN from their physician or physician designee based on the following criteria: bilateral (i.e., present on both sides of the body), abnormal sensory symptoms in their feet or legs (e.g., hot/burning pain, sharp/shooting pain, numbness, tingling, cramping).
- 3. Report at least 1 non-painful symptom associated with CIPN in their lower limbs (e.g., tingling, burning that isn't reported as painful, numbness)
- 4. Report at least 2 of the following symptoms in their lower limbs (at their worst) as at least 4 out of 10 on a 0 10 NRS: hot/burning pain, sharp/shooting pain, numbness, tingling, cramping at Visit 1 (i.e., Week -1). Use the CIPN Symptom Inventory Week Recall form (questions 1-5 ONLY) to assess these symptoms at screening.
- 5. Be willing and able not to start any new analgesic medications or change the dosages of any current analgesic medications (except acetaminophen (Tylenol) or NSAIDs (i.e., ibuprofen (Advil, Motrin), Naproxen (Aleve)) for the duration of the study.
- 6. Be able to read English (i.e., is not illiterate, can speak English, and is not blind).
- 7. Be at least 18 years of age.
- 8. Have access to a smart phone or device with an Apple or Android operating system that can be used to access the TENS device's App and ability to connect to the internet on a daily basis during the trial.

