## 5.3 Schedule of study procedures

# 5.3.1 Screening / Consent Visit (Day -7; -2/+3 days) (approximately 1 hour)

Eligible participants who provide informed consent will be registered and given the daily diary of CIPN symptoms and rescue pain medication consumption, and trained on how to complete it at home during the Baseline Week (i.e., between the Screening and Baseline Visits). They will complete the CPM test and lower limb sensation test. Chemotherapy treatment notes will be collected for all consented participants.

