## 5.3.3 Baseline Visit (Day 0) (approximately 1 hour)

All participants will be randomized according to procedures in **Section 5.3.4** after they arrive for the baseline visit. They will complete the PROs, balance tests, CPM test, and lower limb sensation test. At this time the participants will be given the TENS device (see **Section 5.2** for details of the device) and sufficient electrodes for 6 weeks of the study. They will be trained on how to use the TENS device. Using a standardized script to limit variation in expectations, the unblinded coordinator will lead all participants through the calibration process to identify their ideal intensity setting. The unblinded coordinator will train the participants on how to use the device at home. The unblinded coordinator will also download the Quell Health Account App to the participant's smartphone or other device (e.g., iPad) and create a Quell Health Account using a de-identified Study Email for the participant. The Study Email will be NCORP19085xxx[xxx=participant ID number]@mail.com.

The coordinator will then train the participant to use the App to start the TENS therapy and to open the App at least 1x per day when their mobile device or tablet is connected to the internet so that their deidentified usage data will be uploaded to the cloud. Participants will be asked not to modify settings in the App other than the intensity on the main screen for the 6 weeks of the study. The usage data (i.e., number of sessions per day, time the device is on the skin, and the intensity of the last session that occurred before connecting the device to the internet) will be downloaded from the Quell Health Account by the TENS device manufacturer and provided to the research team for use in promoting adherence (see **Section 5.3.7 Phone calls**). The participants will be given a daily diary to complete during Weeks 4 (i.e., day 21 - 28) and 6 (i.e., day 35 - 42) in which they will record their daily symptoms and rescue pain medication consumption.

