# 5.3.6 At home procedures (Days 21-28; 35-42)

Participants will complete a daily diary including the CIPN Symptom Inventory and consumed rescue analgesic medication (i.e., acetaminophen (Tylenol) or NSAIDs). They will be asked to complete it before bedtime when they are not wearing the device during weeks 4 and 6.

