## 10.6 Exploratory Analyses.

(1) ANCOVA analysis as in the primary will be used to investigate the effects of TENS on exploratory outcomes (i.e., balance (SPPB balance subscale), descending inhibition (CPM test), physical function (PROMIS short form), CIPN-interference in daily life, CIPN measured by TNAS and CIPN symptom inventory composite measure, depression and anxiety (PROMIS short forms)) at baseline and at Week 6 visits.

(2) Analysis of variance (ANOVA) or an appropriate non-parametric method (e.g., Wilcoxon test) if the normality assumption is not satisfied will be used to evaluate the between arm differences in participant-perceived changes in CIPN symptoms and participant-perceived change in ability to be active.

(3) Descriptive statistics will be used to characterize the distribution of descending inhibition as measured by CPM at baseline. Additionally, the correlation of descending inhibition with CIPN severity (via CIPN20, TNAS, and symptom NRS scores) will be evaluated using a Spearman's correlations.

(4) To explore the predictive effects of baseline descending inhibition on response to TENS, ANCOVA analysis will be used to investigate whether baseline descending inhibition predicts the effect of TENS on CIPN. The model will include CIPN20 at Week 6 as the outcome, baseline CPM test result, treatment group, and baseline CPM test result x treatment group interaction as factors, and study site and the baseline CIPN20 score as covariates.

(5) To explore mechanistic associations between changes in descending inhibition and CIPN symptoms, we will use mediation analysis technique (the method initially formalized by Baron and Kenny, extended to clinical trial settings by Kraemer, and methodologically updated by MacKinnon et al.). Specifically, we will use path modeling to estimate indirect (mediation) effects of changes in the CPM test on CIPN symptoms, and bootstrapping to estimate the 95% confidence intervals. The MPlus software will be utilized.

(6) The proportion of participants who decreased "as-needed" usage of acetaminophen and NSAIDs (defined as taking acetaminophen or NSAIDs, on average, at least 30% fewer days per week in the last week of the trial compared to the baseline week) will be compared by groups using a Chi-Square test.

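### Section 10.4 adjusts and subgroups on a fall in acetaminophen/NSAID use that is known only after randomisation, so those results may not estimate the total TENS effect, and any bias could go either way

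*Combined protocol and SAP*

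**What the plan says.** The primary model in Section 10.4 is an ANCOVA of Week 6 CIPN20 on treatment, site and baseline CIPN20. The section then names cancer type, chemotherapy class and analgesic consumption. The last is coded as a ≥30% versus <30% "decrease in number of days acetaminophen and/or NSAIDs were taken), we will add these factors to the above model for sensitivity analyses". The same three factors define subgroups: "We will also perform subgroup analyses separately based on these factors to identify possible differential intervention effects". The stated use of the subgroup results is to help design a later study. No caveat separates the third factor from the other two, and no time window is given for the decrease.

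Section 10.6(6) takes a reduction in the same drugs as an outcome, compared between arms by a chi-square test. It is defined as "on average, at least 30% fewer days per week in the last week of the trial compared to the baseline week".

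On timing, Section 5.3.3 (Day 0) states: "All participants will be randomized according to procedures in" Section 5.3.4. The footnote to Table 10 states: "Daily diary will be completed during the week between the Screening and Baseline visits (collected at the Baseline Visit) and during Weeks 4" and 6.

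These drugs may vary on study. Section 3.1, item 5, bars changes in "dosages of any current analgesic medications (except acetaminophen (Tylenol) or NSAIDs", and Section 5.3.6 has participants record "consumed rescue analgesic medication (i.e., acetaminophen (Tylenol) or NSAIDs" in the diary during treatment.

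**The concern.** Cancer type and chemotherapy class are settled before randomisation, so adjusting for them or splitting by them keeps the randomised comparison. A decrease in analgesic days is not settled then, because TENS may itself cause it. Holding it fixed can remove part of the treatment effect. It can also mix in the effect of cutting the drugs, or create an association through whatever else drives both drug use and CIPN20.

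The primary aim is to obtain efficacy estimates for a phase III design. A gap between the adjusted and primary estimates could be read as an influence of analgesic use, when the model cannot tell relief that lowers use from worsening after drugs are cut. If TENS changes use, a subgroup contrast compares people sorted partly by their response. Whether or not there is bias, nobody can be placed in these subgroups at enrolment, so they cannot guide phase III eligibility or stratification.

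**Working it through.** **1. Is the factor post-randomisation?** A decrease needs a baseline and a later value. The baseline diary ends at the Baseline Visit, when randomisation takes place. The only later diaries are in Weeks 4 and 6, both on treatment. Whichever of these Section 10.4 intends, the factor is unknown at randomisation.

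**2. Is it the Section 10.6(6) outcome?** The drugs, the counting of days and the 30% threshold all match. Section 10.4 gives no window, so this is an inference, though a strong one.

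**3. When does conditioning on it bias the total effect?** Both of these must hold: TENS changes use, and the change is related to Week 6 CIPN20 within arm given baseline CIPN20. If TENS does not change use, the estimates need not be biased.

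**4. Size.** The plan has no figure on this point to reproduce. Only the 0.40 SD effect and the 126 evaluable participants come from Section 10.3. Everything else is assumed. Effects are shown as benefit.

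- Baseline B has SD 1. Week 6 score: Y0 = 0.5·B − 0.40·T + e, with within-arm SD 1.
- Latent tendency to cut the drugs: M = −ρ·(Y0 − B) + noise. A direct TENS effect on use, where present, adds 0.3·T.
- D = 1 for the top 30–50% of M (40% where a direct effect is included). All participants are users.
- Y = Y0 + k·D, where k is any worsening caused by cutting the drugs.
- Total effect: regress Y on T and B. Adjusted effect: regress Y on T, B and D. There are 2,000,000 draws per setting.

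| Scenario | Total (SD) | Adjusted (SD) |
|---|---|---|
| Relief lowers use; ρ = 0.3 / 0.5 / 0.7; k = 0 | 0.40 | about 0.38 / 0.35 / 0.30 |
| Relief plus direct TENS effect on use; same ρ; k = 0 | 0.40 | about 0.34 / 0.28 / 0.20 |
| Direct effect on use only (34% vs 46% decrease); k = 0.2 / 0.5 / 0.8 | 0.38 / 0.34 / 0.31 | 0.40 |
| Direct effect on use only; k = 0 | 0.40 | 0.40 (no bias) |

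The third row can be checked by hand. Total = 0.40 − k × (0.46 − 0.34) = 0.40 − 0.12k, which gives 0.376, 0.340 and 0.304. This agrees with the simulation to within rounding of the two proportions.

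Mixed cases fall in between. With relief at ρ = 0.5, 40% decreasing and k = 0.2 / 0.5 / 0.8, the total is 0.384 / 0.361 / 0.337 against 0.351 adjusted, so the difference changes sign.

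Fewer users shrink the relief-only effect. With 50% users, and non-users coded as no decrease, the adjusted values are 0.39–0.40 / 0.38 / 0.37. That coding is an assumption, because a percentage decrease is undefined for someone with no baseline use and Section 10.4 gives no rule.

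**5. Subgroups.** In a separate relief-only run (residual SD 1, 34% vs 44% decreasing), a total of 0.40 became 0.28 adjusted, with 0.29 and 0.26 in the two subgroups.

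**6. Scale.** The primary standard error is about 2 × √(1 − 0.5²) / √126 = 0.154, and 0.153–0.157 in simulated trials of 126, so about 0.155 SD. The largest shift in the table is 0.40 − 0.20 = 0.20 SD, or 0.20 / 0.155 = 1.3 standard errors. Raising the baseline correlation to 0.7 in the relief-only case at ρ = 0.7 gives 0.29 adjusted. The standard error there is 2 × √0.51 / √126 = 0.127, so the shift is 0.11 / 0.127 = 0.87 standard errors. The size depends on the scenario chosen.

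**The case against.** The strongest reply is that Section 10.4 never says these runs estimate the total TENS effect. The primary ANCOVA does that, and the extra factors are there to explore. Whether changed rescue use explains or masks a result is a fair descriptive question. These are sensitivity and exploratory analyses in a phase II trial run at a two-sided 20% level, with no decision rule resting on them.

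Much of this stands. It limits the seriousness, and it means an adjusted model could be kept if it is labelled for what it is. It does not rescue the subgroups, which are meant to show for whom TENS works and to inform the next trial. Nor does it make the adjusted model a check on the primary result, since the two may target different quantities.

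A reader might infer that adjustment must understate TENS. The documents do not support that: they hold no data on how TENS, drug use and CIPN20 are linked, and the third scenario goes the other way. A reader might also infer from the milder scenarios that the bias is always small beside the standard error. That is not supported either, since other equally untested assumptions give more than one standard error.

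**Conclusion.** The point holds in conditional form. The factor is post-randomisation on any reading of the diary schedule, and Section 10.4 uses it without caveat for both adjustment and subgroups. Bias arises only if TENS changes acetaminophen/NSAID use and that change is related to Week 6 CIPN20 within arm given baseline CIPN20. It attenuates the effect if relief lowers use, and exaggerates it if TENS lowers use and cutting the drugs worsens CIPN20. The sizes above rest wholly on assumed links and are neither estimates nor limits.

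It would be wrong to read this as a flaw in the main result. The primary ANCOVA has no analgesic term and is unaffected, as are separate analyses by cancer type and chemotherapy class. Section 10.4 does not say whether the three factors enter together; a single model holding all three would carry the problem. The harm is to interpretation and phase III planning, and it is worth correcting before the analysis.

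**What to change.** In Section 10.4:

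- Form no subgroups on the on-treatment decrease. Keep it as the Section 10.6(6) outcome.
- In the sensitivity model, replace it with acetaminophen/NSAID days per week in the baseline week. A per-week rate is needed because the screening window (Day −7, −2/+3 days) lets that diary run from about 4 to 9 days.
- Examine differential effects through a treatment-by-baseline-use interaction, reported as an estimate with a confidence interval.
- If a model adjusted for on-study use is kept, label it descriptive, state that it does not estimate the total TENS effect, and say how participants with no baseline use are coded.

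The first and last items are the essential ones. No new data are needed, since Section 5.3.1 already provides for the "daily diary of CIPN symptoms and rescue pain medication consumption, and trained on how to complete it at home during the Baseline Week". Section 10 is part of the protocol, so this is a small amendment needing DCP and CIRB approval under Section 11.3.

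There are two downsides. Baseline use does not address what happens to drug use on study. The interaction is also imprecise: for any use versus none, with half the 126 participants users (31.5 per cell) and baseline correlation 0.5, its standard error is about √(4 × 0.75 / 31.5) = 0.31 SD.
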